### **Pregnancy Follow-Up Reports**

All pregnancies must be followed-up until an outcome is determined. Follow-up Pregnancy Reports must be submitted to the UCL CTC by fax within **7 calendar days** of learning of the outcome. Reports must include an evaluation of the possible relationship of the trial treatment to the pregnancy outcome. Consent to report information regarding pregnancy outcomes must be obtained from the mother.

### **SAEs During Pregnancy**

Any SAE occurring in a pregnant patient must be reported using the trial specific SAE Report, according to SAE reporting procedures.

### **Pregnancy Report Processing at the UCL CTC**

The UCL CTC will submit Pregnancy Reports to MREC should the pregnancy outcome meet the definition of a SUSAR.

# 7. ETHICAL CONSIDERATIONS AND APPROVAL

## 7.1 Ethical considerations

FoRT is a randomised controlled trial. Therefore neither the patients nor their physicians will be able to choose the patient's treatment. Randomisation will be stratified by histology (follicular lymphoma vs. marginal zone lymphoma), and whether treatment is being given with curative or palliative intent. This is to ensure that the groups of patients receiving each of the different treatments are similar.

The study will abide by the principles of the Declaration of Helsinki.

# 7.2 Ethical approval

The protocol will be approved by the Cambridgeshire 4 Research Ethics Committee (formerly the Eastern MREC), and in addition Site Specific Approval must be obtained at each institution before patients are entered at that site.

The patient's consent to participate in the trial should be obtained after a full explanation has been given of the treatment options, including the conventional and generally accepted methods of treatment. Patients should be given sufficient time after being given the trial patient

information sheet to consider and discuss participation in the trial with friends and family. A contact number should be given to the patient should they wish to discuss any aspect of the trial. Following this, the randomising investigator should determine that the patient is fully informed of the trial and their participation, in accordance with ICH GCP guidelines. Patients should always be asked to sign a consent form. One copy should be given to the patient, one copy should be kept with patient's hospital notes and one copy should be kept in the local investigator's file.

The right of the patient to refuse to participate in the trial without giving reasons must be respected. After the patient has entered the trial, the investigator must remain free to give alternative treatment to that specified in the protocol, at any stage, if he/she feels it to be in the best interest of the patient. However, the reason for doing so should be recorded and the patient will remain within the trial for the purpose of follow up and data analysis according to the treatment option to which he/she has been allocated. Similarly, the patient must remain free to withdraw at any time from the protocol treatment without giving reasons and without prejudicing his/her further treatment.

# 8. INDEMNITY

**Non-negligent harm**: University College London, as Sponsor, holds insurance cover that will provide compensation for injury caused by participation in this clinical trial without the need to prove negligence on the part of University College London. Participants who sustain injury and wishing to make a claim for compensation should do so in writing to the Chief Investigator in the first instance.

**Negligent harm**: Participants in this clinical trial are also able to seek compensation via a negligent harm route but this would involve proving negligence on the part of University College London. Insurance cover is held by University College London to cater for this but it is expected that any claim for compensation would be via the non-negligent harm route by virtue of compensation being paid without the need to prove negligence. However, as this clinical trial is being carried out in a hospital, the hospital continues to have a duty of care to the participant of the clinical trial. University College London does not accept liability for any breach in the hospital's duty of care, or any negligence on the part of the employees of hospitals. This applies whether the hospital is an NHS Trust or not. This does not affect the participant's right to seek compensation via the non-negligence route.

# 9. TRIAL COMMITTEES

# 9.1 Trial Management Group (TMG)

A Trial Management Group (TMG) will be formed comprising the Chief Investigator, other lead investigators (clinical and non-clinical) and members with specific interest (e.g. nurses; radiographers). The TMG will be responsible for the day-to-day running and management of the trial and will meet approximately every six months but may convene more often by other means to advise the CI and UCL CTC in the promotion and running of the trial.

# 9.2 Trial Steering Committee (TSC)

The role of the TSC is to provide overall supervision for the trial and provide advice through its independent Chairman. The ultimate decision for the continuation of the trial lies with the TSC. Members of the TSC are currently being appointed. It will meet at least annually and will receive reports from UCL CTC, CI and IMDC.

# 9.3 Independent Data Monitoring Committee (IDMC)

The Independent Data Monitoring Committee will meet at least annually, with interim analysis reports from UCL CTC, to give advice on continuing recruitment. A recommendation to discontinue recruitment (in all patients or in selected subgroups) will be made only if the result is likely to convince a broad range of investigators including participants in the trial and the general clinical community. If a decision is made to continue, the IDMC will advise on the frequency of future reviews of the data on the basis of accrual and event rates. The IDMC will make recommendations to the TSC as to the continuation of the trial. Details of the interim analysis and monitoring are provided in the IDMC charter and in section 5.5.

[figure not shown]

Figure 2: Diagram of relationships between trial committees

# 10. PUBLICATION

Publication will follow the rules of the NCRI lymphoma CSG. Authorship will include the Chief Investigator, trial statistician, a representative of UCL CTC, a member of the central histopathology review team and one additional author from each site entering more than 5% of the total patients.

### APPENDIX 1: HEALTH ECONOMIC QUESTIONNAIRE

\*The EQ-5D questionnaire is to be completed before each clinic visit from the point of registration and randomisation through to the final follow up visit.

Health Questionnaire

(English version for the UK) (validated for use in Eire)

1

By placing a tick in one box in each group below, please indicate which statements best describe your own health state today.

Mobility	
I have no problems in walking about	
I have some problems in walking about	
I am confined to bed	
Self-Care	
I have no problems with self-care	
I have some problems washing or dressing myself	
I am unable to wash or dress myself	
Usual Activities (e.g. work, study, housework, family or leisure activities)	
I have no problems with performing my usual activities	
I have some problems with performing my usual activities	
I am unable to perform my usual activities	
Pain/Discomfort	
I have no pain or discomfort	
I have moderate pain or discomfort	
I have extreme pain or discomfort	
Anxiety/Depression	
I am not anxious or depressed	
I am moderately anxious or depressed	
I am extremely anxious or depressed	

To help people say how good or bad a health state is, we have drawn a scale (rather like a thermometer) on which the best state you can imagine is marked 100 and the worst state you can imagine is marked 0.

We would like you to indicate on this scale how good or bad your own health is today, in your opinion. Please do this by drawing a line from the box below to whichever point on the scale indicates how good or bad your health state is today.

> Your own health state today

Best imaginable health state 100 9重0 7≢0 5≢0 0 Worst imaginable health state

3

Because all replies are anonymous, it will help us to understand your answers better if we have a little background data from everyone, as covered in the following questions.

1.	Have you experienced serious illness?	Yes	No	
	in you yourself			PLEASE TICK
	in your family			APPROPRIATE
	in caring for others			BOXES
		7		
2.	What is your age in years ?	_		
3.	Are you:	Male	Female	PLEASE TICK
				APPROPRIATE BOX
4.	Are you:			
	a current smoker			5. 5. 5. 5. T.O.
	an ex-smoker			PLEASE TICK APPROPRIATE
	a never smoker			BOX
5.	Do you now, or did you ever, work in	Yes	No	
	health or social services?			PLEASE TICK APPROPRIATE BOX
	If so, in what capacity?			
6.	Which of the following best describes			
	your main activity?			
	in employment or self employment			
	retired			
	housework			
	student			DI EARE TIOK
	seeking work			PLEASE TICK APPROPRIATE
	other (please specify)	-		BOX
7.	Did your education continue after	Yes	No	
	the minimum school leaving age?			DI FACE TION
				PLEASE TICK APPROPRIATE
8.	Do you have a Degree or equivalent	Yes	No	BOX
	professional qualification?			PLEASE TICK
	•			APPROPRIATE BOX
9.	If you know your postcode, would you please	write it her	е	

4

#### APPENDIX 2: RTOG RADIATION MORBIDITY SCORING CRITERIA

#### **EXPECTED ADVERSE EVENTS DUE TO RADIOTHERAPY**

The RTOG criteria for scoring acute and late radiation morbidity will be used to assess adverse events in the FoRT trial. As the FoRT trial involves comparatively low doses of radiotherapy, more severe reactions to radiotherapy will not be regarded as expected for the purposes of the study.

Because radiotherapy is a localised treatment, when assessing the relatedness of an adverse event to protocol treatment, the proximity of the affected area to the radiotherapy target field should be taken into consideration.

Grade 1 and 2 toxicity are regarded as expected for low dose radiotherapy (≤24Gy).

Grade 3, 4 and 5 toxicity are regarded as unexpected for the purposes of this trial.

#### **Acute Radiation Morbidity Scoring Criteria**

The RTOG acute radiation morbidity scoring criteria should be used to assess acute toxicity at visit 2 (4 weeks post randomisation)

	0	1 (expected for FoRT)	2 (expected for	(not expected for	4 (not expected for
SKIN	No change over baseline	Follicular, faint or dull erythema/ epilation/ dry dequamation/ decreased sweating	FoRT) Tender or bright erythema, patchy moist desquamation/ moderate edema	FoRT)  Confluent, moist desquamation other than skin folds, pitting edema	FoRT)  Ulceration, hemorrhage, necosis
MUCOUS MEMBRANE	No change over baseline	Injection / may experience mild pain not requiring analgesic	Patchy mucositis which may produce an inflammatory serosanguinitis discharge/ may experience moderate pain requiring analgesia	Confluent fibrinous mucositis/ may include severe pain requiring narcotic	Ulceration, hemorrhage or necrosis
EYE	No change	Mild conjunctivitis with or without scleral injection. Increased tearing	Moderate conjunctivitis with or without keratitis requiring steroids &/or antibiotics/ dry eye requiring artificial tears/ iritis with photophobia	Severe keratitis with corneal ulceration/ objective decrease in visual acuity or in visual fields/ acute glaucoma/ panopthalmitis	Loss of vision (unilateral or bilateral)
EAR	No change over baseline	Mild external otitis with erythema, pruritis, secondary to dry desquamation not requiring medication. Audiogram unchanged from baseline	Moderate external otitis requiring topical medication/ serious otitis medius/ hypoacusis on testing only	Severe external otitis with discharge or moist desquamation/ symptomatic hypoacusis/ tinnitus, not drug related	Deafness

	0	1	2	3	4
		(expected for FoRT)	(expected for FoRT)	(not expected for FoRT)	(not expected for FoRT)
SALIVARY GLAND	No change over baseline	Mild mouth dryness/ slightly thickened saliva/ may have slightly altered taste such as metallic taste/ these changes not reflected in alteration in baseline feeding behaviour, such as increased use of liquids with meals	Moderate to complete dryness/ thick, sticky saliva, markedly altered taste		Acute salivary gland necrosis
PHARYNX & OESOPHAGUS	No change over baseline	Mild dysphagia or odynophagia/ may require topical anaesthetic or non- narcotic analgesics. May require soft diet	Moderate dysphagia or odynophagia/ may require narcotic analgesics/ may require puree or liquid died	Severe dysphagia or odynophagia with dehydration or weight loss (>15% from pre-treatment baseline) requiring N-G feeding tube, IV fluids or hyperalimentation	Complete obstruction, ulceration, perforation, fistula
LARYNX	No change over baseline	Mild or intermittent hoarseness/ cough not requiring antitussive/ erythema of mucosa	Persistent hoarseness but able to vocalise/ referred ear pain, sore throat, patchy fibrinous exudate or mild arytenoid edema not requiring narcotic/ cough requiring antitussive	Whispered speech, throat pain or referred ear pain requiring narcotic/ confluent fibrinous exudate, marked arytenoid edema	Marked dyspnea, stridor or hemoptysis with tracheostomy or intubation necessary
UPPER G.I.	No change	Anorexia with <=5% weight loss from pretreatment baseline/ nausea not requiring antiemetics/ abdominal discomfort not requiring parasympatholytic drugs or analgesics	Anorexia with <=15% weight loss from pretreatment baseline/ nausea &/or vomiting requiring antiemetics/ andominal pain requiring analgesics	Anorexia with >15% weight loss from pretreatment baseline or requiring N-G tube or parenteral support. Nausea or vomiting requiring tube or parenteral support/ abdominal pain, severe despite medication/ hematemesis or melena/ abdominal distention (flat plate radiograph demonstrates distended bowel loops)	Ileus, subacute or acute obstruction, perforation / GI bleeding requiring transfusion; abdominal pain requiring tube decompression or bowel diversion
LOWER GI INCLUDING PELVIS	No change	Increased frequency or change in quality of bowel habits not requiring medication/ rectal discomfort not requiring analgesics	Diarrhea requiring parasympatholytic drugs (e.g. Lotomil)/ mucous discharge not necessitating sanitary pads/ rectal or abdominal pain requiring analgesics	Diarrhea requiring parenteral support/ severe mucous or blood discharge necessitating sanitary pads/ abdominal distention (flat plate radiograph demonstrates distended bowel loops)	Acute or subacute obstruction, fistula or perforation; FI bkeeding requiring transfusion; abdominal pain or tenesmus requiring tube decompression nor bowel diversion

	0	1	2	3	4
		(expected for FoRT)	(expected for FoRT)	(not expected for FoRT)	(not expected for FoRT)
LUNG	No change	Mild symptoms of dry cough or dyspnea on exertion	Persistent cough requiring narcotic, antitussive agents/ dyspnea with minimal effort but not at rest	Severe cough unresponsive to narcotic antitussiveagent or dyspnea at rest/ clinical or radiologic evidence of acute pneumonitis/ intermittent oxygen or steroids may be required	Severe respiratory insufficiency/ continuous oxygen or assisted ventilation
GENITO- URINARY	No change	Frequency or urination or nocturia twice pretreatment habit/ dysuria, urgency not requiring medication	Frequency or urination or nocturia which is less frequent than every hour. Dysuria, urgency, bladder spasm requiring local anaesthetic (e.g. Pyridium)	Frequency with urgency and nocturia hourly or more frequently/ dysuria, pelvis pain or bladder spasm requiring regular, frequent narcotic/ gross hematuria with/without clot passage	Hematuria requiring transfusion/ acute bladder obstruction not secondary o clot passage, ulceration or necrosis
HEART	No change over baseline	Asymptomatic but objective evidence of ECG changes or pericardial abnormalities without evidence of other heart disease	Symptomatic with ECG chabges abd radiologic findings of congestive heart failure or pericardial disease/ no specific treatment required	Congestive heart failure, angina pectoris, pericardial disease responding to therapy	Congestive heart failure, angina pectoris, pericardial disease, arrhythmias not responsive to non- surgical measures
CNS	No change	Fully functional status (i.e. able to work) with minor neurologic findings, no medication needed	Neurologic findings present sufficient to require home case/ nursing assistance may be required/ medications including steroids/ anti-seizure agents may be required	Neurologic findings requiring hospitalization for initial management	Serious neurologic impairment which includes paralysis, coma or seizures >3 per week despite medication/hospitalization required
WBC	>/= 4.0	3.0 - < 4.0	2.0 - < 3.0	1.0 - < 2.0	< 1.0
PLATELETS	>/= 100	75 - < 100	50 - < 75	25 - < 50	<25 or spontaneous bleeding
NEUTROPHILS	>/= 1.9	1.5 - <1.9	1.0 - <1.5	0.5 - < 1.0	<0.5 or sepsis
HAEMOGLOBIN (GM%)	> 11	11 - 9.5	<9.5 - 7.5	<7.5 - 5.0 Packed red cell	
HAEMATOCRIT	>/= 32	28 - < 32	< 28	transfusion required	

GUIDELINES: The acute morbidity criteria are used to score/grade toxicity from radiation therapy. The effects are criteria are relevant from day 1, the commencement of therapy, through day 90. Thereafter the EORTC/RTOG Criteria of Late Effects are to be utilized.

The evaluator must attempt to discriminate between disease- and treatment-related signs and symptoms.

An accurate baseline prior to commencement of therapy is necessary

All toxicity Grade 3, 4 or 5\* must be verified by the Principal Investigator

\* ANY TOXICITY WHICH CAUSED DEATH IS GRADED 5

http://www.rtog.org/members/toxicity/acute.html

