# 1.3 Flow diagram

Figure 1: Trial entry, randomisation and treatment

Assessme	nt	
	ARM A 24 Gy in 12#	ARM B 4Gy in 2#
Visit 1 Baseline	Registration & Randomisation forms	Registration & Randomisation forms
Week 1	Treatment	Treatment
Week 2	Treatment	
Week 3	Treatment	
Week 4	Acute toxicity	Acute toxicity
Week 12 Follow up	Post Treatment Assessment Tumour Assessment Tumour Response Evaluation Late toxicity	Post Treatment Assessment Tumour Assessment Tumour Response Evaluation Late toxicity
Follow up *	Tumour Assessment Late toxicity	Tumour Assessment Late toxicity

\* After the week 12 follow up visit, patients will be assessed at 6 months, 12 months, 18 months, 24 months and annually thereafter until 5 years post randomisation using the above assessments.

An EQ-5D Health Assessment questionnaire must be completed at every visit. Patients will then be followed up yearly for life for monitoring of overall survival.

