# 2.4 Screening procedures and pre-randomisation investigations

Once informed consent has been obtained the Randomisation and Registration CRFs must be completed. Pre-randomisation investigations recommended are a CT scan (neck, chest, abdomen, pelvis) if required or indicated, and a mandatory full blood count. A biopsy is recommended if there is a clinical suspicion of a transformation to high-grade disease.

Patients' disease will be staged using the Ann Arbor system (Appendix 6) prior to randomisation. This information is to be recorded on the registration CRF. Investigators will be required to stipulate on the registration form whether treatment is to be given with curative or palliative intent.

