### 3.9 Procedures for assessing safety

Acute toxicity will be determined at 4 weeks post randomisation using the RTOG Acute Radiation Morbidity Scoring Schema (Appendix 2). The late toxicity will then be assessed at every visit thereafter using the RTOG/EORTC Late Radiation Morbidity Scoring Schema (Appendix 2). See section 6 on Safety Reporting for more information.

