## **Reporting Procedures**

### **All Adverse Events (AEs)**

All adverse events that occur between informed consent and the end of the trial must be recorded in the patient notes and the trial CRFs. Information regarding dates of event onset and resolution, outcome, severity and causality for the trial treatment must be recorded. Those meeting the definition of a Serious Adverse Event (SAE) must also be reported to the UCL CTC using the trial specific SAE Report (see Serious Adverse Events section for details).

Pre-existing conditions do not qualify as adverse events unless they worsen.

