# **APPENDIX 4: FOLLOW UP SCHEDULE**

Table 3 shows the visit schedule for the FoRT trial

Table 3: FoRT trial visit schedule

Visit number	Timepoint
1	Baseline
2	4 weeks post randomisation
3	12 weeks post randomisation – response assessment
4	6 months post randomisation
5	1 year post randomisation
6	18 months post randomisation
7	2 years post randomisation
8	3 years post randomisation
9	4 years post randomisation
10	5 years post randomisation

Once the five years of scheduled follow up are completed, patients will be followed up for survival annually until death.

The forms due at each visit are summarised in table 4 below.

Table 4: Forms due at each clinic visit

Form	Details	Compulsory / as required
Registration form	4 pages to be completed at visit 1 and faxed to UCL CTC	Compulsory
Randomisation form	1 page to be completed at visit 1 and faxed to UCL CTC	Compulsory
4-week follow up form	1 page to be posted to UCL CTC within 8 weeks of visit 2	Compulsory
Acute toxicity form	1 page to be posted to UCL CTC to be completed at visit 2 as required and posted to the UCL CTC within 8 weeks of visit 2 along with 4-week follow up form	Only required if patient experienced acute toxicity from radiotherapy
12-week follow up form	4 pages to be posted to UCL CTC within 8 weeks of visit 3	Compulsory
Follow up form	1 page to be completed at visits 4 – 10 and posted to UCL CTC within 8 weeks of visit	Compulsory up to the point of local progression
Late toxicity form	1 page to be completed at visit 3 – 10 as required and posted to UCL CTC within 8 weeks of the relevant visit along with the follow up form	Only required if patient experienced late toxicity from radiotherapy
Disease progression form	1 page to be completed at first progression within the irradiated field	Only required at local progression
Disease progression follow up form	1 page to be completed at all scheduled visits after local progression instead of the follow up form	Compulsory after local progression
Anti-cancer treatment form	1 page to be completed at visits 2-10 as required and posted to UCL CTC within 8 weeks of the relevant visit along with the follow up form	Only required if patient received cancer treatment other than their trial radiotherapy
Hospital admission form	1 page to be completed at visits 2-10 as required and posted to UCL CTC within 8 weeks of the relevant visit along with the follow up form	Only required if patient is admitted to hospital

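### Acute toxicity grading is said to need a pre-treatment baseline, but no RTOG symptom score is scheduled before week 4, so attribution rests on unblinded site judgement

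*Protocol*

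**What the plan says.** Protocol Appendix 2, in the guidelines below the acute scoring table: "An accurate baseline prior to commencement of therapy is necessary". The same guidelines ask the evaluator to try to tell disease-related from treatment-related signs.

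Section 3.9 fixes the timing: "Acute toxicity will be determined at 4 weeks post randomisation using the RTOG Acute Radiation Morbidity Scoring Schema". Late toxicity is scored at each visit after that. Appendix 2 likewise assigns the acute criteria to visit 2 and the late schema to visit 3 onward.

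For visit 1, the flow diagram in section 1.3 lists "Registration & Randomisation forms", and its footnote adds the EQ-5D at every visit. Table 4 in Appendix 4 describes the acute toxicity form as "1 page to be posted to UCL CTC to be completed at visit 2 as required" and asks for it only where the patient had acute toxicity caused by radiotherapy. The late form, for visits 3 to 10, carries the matching condition.

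Section 6, on all adverse events: "Pre-existing conditions do not qualify as adverse events unless they worsen". Section 2.4 lists, among the pre-randomisation investigations, "a mandatory full blood count".

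Section 1.2 describes the trial as open. Section 5.2 makes acute and late toxicity secondary outcomes, and section 5.4 compares toxicity between arms by chi-squared or Mann-Whitney tests.

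**The concern.** The grading scale works by comparison with the patient's earlier state, and the Protocol says so, yet it does not schedule a record of that state. Palliative patients are eligible because of tumour bulk or anatomical position (section 2.1), and section 1.4.1 describes such masses as symptomatic. Cough, difficulty in swallowing or bowel symptoms present before the first fraction can match a description in the table.

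At week 4 the site must decide which symptoms radiotherapy caused. It knows the allocated dose and has no scheduled score to compare with. If pre-existing symptoms are counted alike in both arms, the difference between arms shrinks. If they are discounted more readily in one arm, a difference can appear or disappear for reasons unrelated to treatment. An analysis plan can define change from baseline, but it cannot recover a baseline that was not collected.

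**Working it through.** The Protocol gives no toxicity rate, no symptom prevalence and no power for toxicity, so there is no stated figure to reproduce. The check is a reading of the sections against each other, followed by an illustration on assumed values.

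**1. Does the acute scale need a baseline?** Yes. All 13 organ rows of the acute table define grade 0 as no change. Seven of them (skin, mucous membrane, ear, salivary gland, pharynx and oesophagus, larynx, heart) name baseline explicitly. Upper GI grades use weight loss from the pre-treatment value, and the lowest genito-urinary grade uses a multiple of the pre-treatment habit. The five blood rows use absolute cut-offs.

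**2. Does the late schema need one?** The baseline sentence belongs to the acute guidelines. In the late schema, grade 0 means that the sign is absent, not that it is unchanged. A long-standing dry mouth or hoarseness therefore fits a grade at visit 3 unless someone recalls that it was there before.

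**3. Is a baseline score scheduled?** Sections 1.3, 2.4 and 3.9, Appendix 2 and Table 4 contain no RTOG score at visit 1. The records that are due then are the registration and randomisation forms, a full blood count and the EQ-5D. The EQ-5D is generic and yields no organ grade.

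**4. What could follow? (illustration only)** Assumed inputs: true toxicity t in each arm; look-alike pre-existing symptoms in a share b of patients, independent of toxicity; a share d of those discounted by the site. From the Protocol: 650 patients at 1:1, so 325 per arm.

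Observed rate = 1 − (1 − t)(1 − b(1 − d)).

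Power is the normal approximation at two-sided 5%, with p̄ the mean of the two observed rates pA and pB and n = 325: Φ{(|pA − pB| − 1.96√[2p̄(1 − p̄)/n]) / √[(pA(1 − pA) + pB(1 − pB))/n]}.

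Dilution, with t = 40% v 30% and d = 0 in both arms. The difference is multiplied by (1 − b):

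| b | Observed rates | Difference | Power |
|---|---|---|---|
| 0 | 40% v 30% | 10 points | 76% |
| 10% | 46% v 37% | 9 points | 64% |
| 20% | 52% v 44% | 8 points | 53% |
| 30% | 58% v 51% | 7 points | 43% |

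For b = 10%: 1 − 0.60 × 0.90 = 0.46 and 1 − 0.70 × 0.90 = 0.37.

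Differential attribution, with t = 30% in both arms and discounting in one arm only. False difference = (1 − t) × b × d = 0.70bd:

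| b | d = 25% | d = 50% |
|---|---|---|
| 10% | 1.75 points | 3.5 points |
| 20% | 3.5 points | 7.0 points |
| 30% | 5.25 points | 10.5 points |

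If there is no true difference and both arms are treated alike, the false difference is zero at every b.

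**The case against.** The strongest reply is that the Protocol already forbids the error. Section 6 excludes pre-existing conditions unless they worsen. Appendix 2 asks for disease signs to be separated from treatment signs and for closeness to the field to be considered. Table 4 limits the toxicity forms to effects of radiotherapy. A reader might infer that pre-existing symptoms are graded as toxicity under this plan; these rules do not support that. What stands is narrower: each rule presupposes a known starting point, and none schedules its recording. Collecting adverse events from consent captures new events, not the state at consent.

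A reader might also infer that low blood counts present at entry go unrecognised. That does not follow, because a count is mandatory before randomisation. The gap on that side is a different one: no count is scheduled at week 4, so the blood rows can be graded only where a site happens to take one.

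Nor is visit 1 limited to registration and randomisation paperwork, since the EQ-5D is also due. The registration form runs to four pages and its content is not shown; it may record presenting symptoms. Appendix 2 does not say that the baseline must be an RTOG form, and clinic notes might serve. These points lower the confidence but leave the scheduling gap in the Protocol text.

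It is also fair to say that equal counting in randomised arms only dilutes, that large true differences would survive it, and that how grades above baseline are analysed could be left to an analysis plan. The visit-1 assessment could not.

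**Conclusion.** The point holds with moderate confidence. The Protocol calls a pre-treatment baseline necessary for acute grading and schedules no RTOG symptom score before visit 2. In an open trial, attribution at week 4 and later therefore has no scheduled comparator. The likely effect is dilution; bias arises only if sites attribute symptoms differently by arm, which the documents neither show nor rule out.

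The size cannot be stated. The 7-to-9-point and 2-to-10-point figures depend wholly on assumed rates, on independence of old symptoms and toxicity, and on pre-existing symptoms being counted despite the rule in section 6. They show direction and scale, not an estimate for this trial.

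Only the secondary outcomes of acute and late toxicity are touched; the primary endpoint and the sample size are not. A reader might also infer that lower toxicity is the main case for 4Gy and that this gap undermines it. Sections 1.5 and 1.6 rest the rationale on efficacy with fewer fractions and on linear-accelerator capacity, so the point should not carry that weight. It is a worthwhile, inexpensive correction rather than a threat to the trial's main conclusion.

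**What to change.** In section 3.9, Figure 1 and Table 4, add the existing one-page RTOG acute form at visit 1, after consent and before randomisation, covering the organs in or near the planned field. If the registration form already records these symptoms, a cross-reference to it is enough. In section 5.2, define acute and late toxicity as a grade that exceeds the patient's own pre-treatment state.

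The cost is one page and a few minutes at enrolment, with no new test. Scoring before randomisation means the baseline is recorded without knowledge of the arm. The change does not remove unblinded judgement at week 4, but it gives that judgement a recorded starting point against which it can be checked.
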